**Open Label Study of Subcutaneous Immunoglobulin (SCIg)
in Myasthenia Gravis**

NCT02100969

February 22, 2019

Data Analysis Plan and Statistical Considerations:

1. Analysis of Primary Outcome:

At the end of the 9-week IVIg screening phase, baseline QMG scores of all the patients will be recorded. At the end of SCIg experimental treatment phase (Week 12), the QMG score will be captured and compared to Week 0. If the increase in QMG scores from Week 0 to Week 12 in the experimental treatment phase is found to be no more than 3 points, then they will be considered to be a 'success' in terms of their response. We hypothesize that the positive response rate of these patients is at least 70%. Allowing a margin of 5%, our hypotheses are formally stated below:

Null hypothesis H_0 : Proportion of patients whose QMG scores are increased by more than 3 points at the end of the SCIg treatment phase ≤ 0.65

Alternate hypothesis H_A : Proportion of patients whose QMG scores are increased by no more than 3 points at the end of the SCIg treatment phase > 0.65

This hypothesis will be tested using a one sided one sample test of proportions with the normal approximation, at the 5% significance level. We will also report a 95% confidence interval for the true proportion of subjects who experience a 'success' as with a sample size of 25 patients, we will have a margin of error of 0.19. In the experimental treatment phase, patients who either experience treatment failure (as previously defined on pg. 22) or clinical deterioration (as defined above on pg. 22) will be withdrawn before Week 12 and we will therefore impute for both non-positive responses at Week 12, a discrete QMG score increase of more than 3 points. For example, if the largest deterioration score observed is 8, then a QMG score ranging between 4 and 8 will be imputed at Week 12. Although we do not expect many missing observations at Week 12 of the SCIg phase, the outcomes recorded at these intermediate time points will allow us the ability to impute data at this endpoint. Specifically, in the case where no outcome is available for a subject at Week 12 due to the subject's perception of a worsened condition, we will impute for this subject a QMG score increase at Week 12 of more than 3 points. In cases where subjects refuse to proceed to Week 12 or are lost to follow-up even though they were responding well on the treatment (as evidenced by the intermediate measurements), we will impute their Week 12 observation using the last observation carried forward (LOCF) approach. We will complement our LOCF approach with sensitivity analyses covering the following alternate approaches: (1) Multiple imputation with 5 replicates per imputation to account for the uncertainty inherent to the imputation (2) Mixed model calculations accounting for the trend in QMG values over time (3) Best case and worst-case scenarios.

2. Additional Exploratory Analysis of Primary Outcomes:

Additional exploratory analysis will be carried out treating QMG scores at baseline, Week 4, Week 8 and Week 12, as a continuous response variable. Descriptive statistics will be reported using means and standard deviations if the distribution of QMG scores is found to be normal and using medians and interquartile range if they are found to be non-normal. One advantage of reporting scores at the intermediate weeks is that it will allow us to assess whether or not some patients on SCIg stabilize early in terms of the QMG scores. It will also allow us to study the trend over time in an exploratory manner. We will further complement our exploratory analysis by conducting a two-sided non-parametric signed rank test in order to assess whether the QMG scores changed significantly after switching from IVIg to SCIg. Also, we will dichotomize the QMG into two groups

(high and low) based on clinically relevant thresholds and compare the differences in proportions at end of study and baseline.

3. Analysis of Secondary Outcomes:

Analysis of secondary outcome measures as listed in the Aims section such as MG-ADL, MG QOL-15, the MG composite score and TSQM will primarily be conducted only for those who complete the study. We will conduct a two-sided signed-rank test to assess whether these scores changed significantly from baseline (Week 0) to Week 12. In case of missing values for the MG-ADL, MG QOL-15, and the MG composite score in cases where subjects refuse to proceed to Week 12 even though they were responding well on the treatment (as evidenced by the intermediate measurements) or are lost to follow-up, we will impute their Week 12 observation using the last observation carried forward (LOCF) approach. We will also report the proportion of subjects enrolled in the subcutaneous experimental treatment study phase (Week 0 to Week 12) fulfilling our definition of improvement (as mentioned on pg. 24) along with a 95% confidence interval. We will compare between the two phases the percent of subjects meeting the definition of deterioration, worsening, stability and improvement. We will analyze the effect of prednisone dosage (Increase vs Not Increased) on clinical improvement (Yes vs No) using a 2x2 Fisher's exact test in the SCIg phase of the study by comparing dose levels at Week 12 to Week 0 for those patients who complete Week 12 of the study. To do this, we will ask the patients at Week 0, Week 4, Week 8 and Week 12 about their prednisone dosage levels. Those patients who exit the study prematurely due to deterioration before Week 12 will be excluded from this Fisher's test calculations. In the event that the Week 12 prednisone dose observation is missing even when patients have completed Week 12 (QMG or MGADL done), we will use the LOCF approach to impute this missing value as long as at the last available assessment, the patient was deemed to be improving (in terms of QMG or MGADL scores as defined under "Subject deterioration, worsening, rescue medication and improvement"). A two-sided signed-rank test will be also conducted to assess whether IgG levels changed significantly between the intravenous screening phase (Week -10 to Week 0) to the subcutaneous experimental treatment study phase (Week 1 to Week 12). All tests will be conducted at the 5% level of significance. For the secondary outcome measures related to monitoring the safety profile of patients between the two study phases, a similar test will be conducted when the safety parameters measured are continuous variables and a one sample test for the difference in proportions will be conducted when they are measured as treatment-related severity rates. The comparison epochs for safety are also between the intravenous screening phase (Week -10 to Week 0) and the subcutaneous experimental treatment study phase (Week 0 [after first SCIg dose] to Week 12). Adverse events occurring in the two phases (mild, moderate/severe) will be summarized using a McNemar's test.

4. Sample Size Considerations:

With a sample size of 25 patients, we have at least 70% power to detect a success rate of 85% or higher using the chi-square test compared to an expected success rate of 65% or lower. We anticipate we will be able to assess efficacy, safety and tolerability of SCIg with the current sample size over 12 weeks and compare that these parameters to the 12-week IVIg phase. The selected sample size will enable us to complete study enrollment with the current number of sites.

MG is a rare disease and MG studies have consistently experienced difficulty enrolling subjects due to a multiplicity of poorly understood reasons.³⁴ In the Methotrexate study of MG and similar to other previous MG studies, enrollment has been a challenge. However, we managed to complete enrollment of 50 subjects by adding sites. In the current SCIg study protocol, the eligible

study population is narrowed due to the inclusion criterion requiring MG cases to be on stable IVIg doses. While 85 to 90% of MG patients are seropositive for either the AchR or MuSK autoantibodies, some of these cases are treated in clinical practice with IVIg maintenance. Based on the pre-site selection feasibility survey, 25 subjects is a reasonable and achievable goal with the selected five sites. If enrollment is found to be slower than predicted, we are ready to add more sites to complete this study.

5. Study Populations:

Safety population: All patients enrolled at baseline constitute the safety population. The subjects in this population will be included in the analysis of adverse events, vital signs, clinical laboratory findings, and other safety data. But for the purpose of statistical analyses, the rates of adverse events experienced by these subjects in the SCIg phase will be compared to the rates experienced during the IVIg phase of the study. Adverse events will be tabulated by treatment group, severity, and perceived relationship to study drug. For each adverse event, the treatment groups will be compared regarding the occurrence of at least one event using the Fisher's exact test. The comparisons will be repeated excluding all mild symptoms. Continuous measures such as vital signs and laboratory test results will be analyzed in a manner similar to that for the primary outcome variable.

Intent to treat population (ITT): Only those patients who receive at least one dose of SCIg are considered to be the primary population which is the same as ITT population. The ITT will be included in the analysis of baseline findings and efficacy results. Only those patients who receive at least one dose of SCIg are considered to be the primary population and the intent-to-treat population.

Unscheduled visits: In the event that there are unscheduled patient visits, we will report the frequency of such visits for the two phases of the study. We will also document the date and reason for such visits and assess if these visits are systematic or random. If occurrence of such visits is due to side effects we will compare the rates of such events across the two phases of the study. Testing at unscheduled visits is done only to check and assess clinical worsening. If no worsening is found, patients will continue to be a part of the study. If a patient experiences a worsening event that does not qualify as clinical deterioration (per pg. 22) and the investigator determines it is safe for that patient to continue, the patient will remain in the study. On the other hand, if a patient experiences a worsening event that qualifies as clinical deterioration the patient will be withdrawn from the study. We will compare the within-person variation to the cross-person variation for the overall data. If the within-person variation is found to be less than the cross-person variation, we will use a LOCF approach to impute the patient's QMG score at the next time point and do a sign rank test on that time point and baseline. On the other hand, if the within-person variation is found to be greater than the cross-person variation, we will impute the observation at the next time point followed by a sign rank test.

SAS 9.4 will be used for all analyses. All data management and statistical analysis will be performed in the Department of Biostatistics at the University of Kansas Medical Center. The Velos Clinical Research Information System (CRIS) will be used at all sites to enter and view data. This will be available to the safety monitors (see below).

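### Minor: with only 5 imputations and no stated seed, the significance verdict of the multiple-imputation check can depend on the seed when the success count is close to the cutoff

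*SAP*

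**What the plan says.** All of this is in SAP section 1 (Analysis of Primary Outcome) and section 4 (Sample Size Considerations).

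- **Endpoint.** A patient whose QMG increase from Week 0 to Week 12 "is found to be no more than 3 points, then they will be considered to be a 'success".
- **Test.** It is a "one sided one sample test of proportions with the normal approximation, at the 5% significance level", against 0.65.
- **Size and power.** "With a sample size of 25 patients, we have at least 70% power to detect a success rate of 85% or higher", "compared to an expected success rate of 65% or lower".
- **Missing Week 12 values.** Treatment failure, clinical deterioration and dropout for perceived worsening count as non-success by rule. Patients who were responding well but refuse to go on, or are lost, get LOCF. The SAP expects few missing values and gives no number.
- **Checks.** "We will complement our LOCF approach with sensitivity analyses covering the following alternate approaches": the first is "Multiple imputation with 5 replicates per imputation to account for the uncertainty inherent to the imputation", the second a mixed model, the third "3) Best case and worst-case scenarios".

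The SAP gives no reason for 5, and no seed, imputation model or pooling rule for the test. I read its wording as five completed data sets (M = 5).

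**The concern.** Each patient is worth 4 percentage points, and the verdict changes between 20 and 21 successes. The design alternative of 85% corresponds to 0.85 × 25 = 21.25 successes, so a result near the line is a likely outcome of this trial. With five random draws per missing patient, the pooled success rate carries Monte Carlo noise that can move the p-value across 0.05 with the same data and the same model.

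At stake is the usefulness of one sensitivity analysis. It is meant to show whether the LOCF success calls hold, and near the cutoff its answer could change on a rerun. With no seed fixed, a rerun also cannot be told apart from a choice of result, which matters somewhat more in an open-label single-arm trial.

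**Working it through.** **1. The plan's own figures.** With n = 25, null rate 0.65 and alternative 0.85, the null standard error is √(0.65 × 0.35/25) = 0.0954. Power = Φ((0.20 − 1.645 × 0.0954)/√(0.85 × 0.15/25)) = 72.7%, so the statement of "at least 70% power to detect a success rate of 85% or higher" reproduces. The margin of error 1.96·√(p(1−p)/25) is 0.187 at p = 0.65 and 0.196 at p = 0.5, in line with the stated 0.19.

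**2. The cutoff.** z = (x/25 − 0.65)/0.0954.

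| Successes | z | one-sided p |
|---|---|---|
| 20/25 | 1.57 | 0.058 |
| 21/25 | 1.99 | 0.023 |

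**3. Pooling.** For M imputations, Q is the mean success proportion, W = 0.65 × 0.35/25 = 0.0091 (null variance), B the between-imputation variance and T = W + (1 + 1/M)B. The statistic (Q − 0.65)/√T is referred to a t distribution with Rubin's degrees of freedom. *Assumptions, not in the SAP:* the number k of patients imputed at random, the observed count, and the imputed success probability q.

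**4. One case by hand: 19/23 observed, k = 2, q = 0.8, M = 5.** There are 10 imputed outcomes, of which j ~ Binomial(10, 0.8) are successes, and Q = (19 + j/5)/25.

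- j ≥ 8: Q is at least 0.824, and every arrangement is significant.
- j = 7: Q = 0.816. Significance needs T below (0.166/1.645)² = 0.0102, that is B below about 0.0009. If the three failures fall in three different data sets, B = 0.3/625 = 0.0005 (significant). If two fall in the same one, B = 0.8/625 = 0.0013 (not significant). The second pattern has probability 40/120 = 1/3.
- j ≤ 6: Q is at most 0.808, not significant.

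P(non-significant) = P(j ≤ 6) + P(j = 7)/3 = 0.121 + 0.201/3 = 0.188, about 19%. In the limit of many imputations, Q = 0.824, B = 2 × 0.8 × 0.2/625 = 0.00051, z = 0.174/√0.00961 = 1.77 and p = 0.038, so the settled verdict is significant.

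**5. Simulation over seeds (null variance, Rubin's rules).**

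| Observed | k | q | Settled p | M = 5 | M = 50 | M = 100 |
|---|---|---|---|---|---|---|
| 19/23 | 2 | 0.80 | 0.038 | 19% non-significant (95% range of p 0.023–0.068) | 0.1% | 0% |
| 19/22 | 3 | 0.65 | 0.031 | 15% non-significant | 0% | 0% |
| 20/24 | 1 | 0.75 | 0.032 | 2% non-significant | 0% | 0% |
| 18/22 | 3 | 0.75 | 0.055 | 37% significant | 18% | 10% |

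The last row is knife-edge: Q = (18 + 2.25)/25 = 0.81, B = 3 × 0.75 × 0.25/625 = 0.0009, T = 0.0100, z = 0.16/0.10 = 1.60, p = 0.055. More imputations reduce the seed dependence there but do not remove it.

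**6. Averaged over possible data at a true rate of 0.85** (q from 0.65 to 0.90, with added uncertainty in q), two seeds give different verdicts at M = 5 with probability 0–2% for one missing patient, 2–12% for two or three, and 10–18% for five. At M = 50 to 100 this is near 0, except in knife-edge settings (about 2–9%).

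**The case against.** - **Five is efficient enough.** Relative efficiency is 1/(1 + γ/M): 98% at M = 5 for a fraction of missing information γ of 0.10, and 96% for 0.20. This stands for the point estimate, and five is not an error as such. It does not address whether the p-value reproduces.
- **Few patients are affected.** The SAP expects few missing values, and patients failing by rule need no draw for the yes/no endpoint. Those left were responding well, so q may be high; for 18/22, 3 missing and q = 0.90, 89% of seeds at M = 5 already agree. This stands, and it is why the point is conditional.
- **Best-case and worst-case bounds cover it.** They need no seed and contain every possible imputation of the missing outcomes. But with 19/23 and 2 missing they are 19/25 and 21/25, on either side of the cutoff, and multiple imputation is what would show the plausible middle.
- **The SAP does not name the variance of its z-test.** With the Wald variance, 20/25 is already significant (p = 0.030). The pattern is the same at the shifted cutoff: for 19/24, 1 missing and q = 0.8, 74% of seeds are significant at M = 5 and 99.5% at M = 100. So under that reading a single imputed patient can suffice.

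A reader might infer that the seed could overturn the trial's primary result. The SAP does not support this: multiple imputation is one of three analyses that accompany LOCF, and the primary verdict comes from LOCF and the failure rules. Nor does the SAP set a p < 0.05 criterion for the check.

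**Conclusion.** The point holds as a minor, optional improvement. With M = 5 and no stated seed, the significance verdict of the multiple-imputation check can depend on the seed if the count lies near the 20/21 line and about two or more patients are imputed. In the two worked cases of that kind with a clear settled verdict, 15% to 19% of seeds fall on the wrong side at M = 5, against at most 0.1% at M = 50. With no imputed patient, or a count clear of the line, there is no practical effect; with one imputed patient it is small under the null-variance test.

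The sizes rest on assumed missingness, assumed imputed success probabilities, the null variance and Rubin's rules, none of which the SAP states. A reader might also infer that five imputations make the whole assessment of missing data unreliable. That goes too far, since the point estimate loses only a few percent of efficiency and the bounds do not depend on random draws.

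**What to change.** In SAP section 1, replace the 5 replicates by at least 100 imputations with a seed fixed in the SAP before the data are analysed. Add one sentence: classify each completed data set by the 3-point rule, pool the success proportion by Rubin's rules, and report the Monte Carlo error of the pooled rate. For 18/22 observed, 3 missing and q = 0.75, that error is √(0.0009/5) = 0.0134 at M = 5 and √(0.0009/100) = 0.0030 at M = 100. The reported error is needed because knife-edge data stay partly unsettled at 100; in such a case the report should say so and not rest on which side of 0.05 the pooled p-value falls.

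The cost is one number, one sentence and negligible computing time. No data collection or primary analysis changes.

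### On the continuous scales the only planned inference on change after the switch is a two-sided signed-rank test, with no interval to show how much worsening is excluded

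*SAP*

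**What the plan says.** SAP section 1 puts the maintenance question patient by patient. Success means that the "increase in QMG scores from Week 0 to Week 12 in the experimental treatment phase is found to be no more than 3 points". The success proportion is tested by a "one sided one sample test of proportions with the normal approximation, at the 5% significance level", and a 95% interval for it is promised.

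Section 2 then treats QMG as a continuous score, as an exploratory analysis. It plans descriptive statistics by visit, a look at the trend over time, a high/low split, and "conducting a two-sided non-parametric signed rank test in order to assess whether the QMG scores changed significantly after switching from IVIg to SCIg".

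Section 3 covers MG-ADL, MG QOL-15, the MG composite and TSQM: "We will conduct a two-sided signed-rank test to assess whether these scores changed significantly from baseline (Week 0) to Week 12". The level is 5%, and the analysis "will primarily be conducted only for those who complete the study".

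Section 3 adds a 95% interval for the proportion improved and a between-phase comparison of the percentages deteriorated, worsened, stable and improved. Neither section plans an interval for a mean or median change. The mixed model in section 1 is listed as a sensitivity analysis for missing data, with no stated estimate or interval for change.

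**The concern.** Patients come from stable IVIg, and the trial asks whether they hold their ground on SCIg. A signed-rank test asks whether the null of no change can be rejected. In a maintenance setting the hoped-for answer is that it cannot, yet in a small sample that is also a common answer when patients have got somewhat worse. A p-value above 0.05 does not separate a change tightly centred on zero from one too imprecise to judge.

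What is at stake is how informative the secondary and exploratory results are. As planned, the report could say whether each scale changed significantly, but not what degree of worsening was excluded.

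The secondary scales have a further weakness. Section 1 says that patients who fail treatment or deteriorate are withdrawn before Week 12. The carry-forward rule in section 3 covers patients lost to follow-up and those doing well who decline to continue; it names no imputation for patients withdrawn for deterioration. The largest worsenings may therefore be missing from these comparisons.

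**Working it through.** **1. The plan's own figures, which concern proportions only.** Section 4 states: "With a sample size of 25 patients, we have at least 70% power to detect a success rate of 85% or higher". The null rate there is 65%.
- Critical proportion, one-sided 5%: 0.65 + 1.645 × √(0.65 × 0.35 / 25) = 0.65 + 1.645 × 0.0954 = 0.807.
- Power at 0.85: Φ[(0.85 − 0.807) / √(0.85 × 0.15 / 25)] = Φ(0.043 / 0.0714) ≈ 72.7%. This agrees with the SAP. Counted in whole patients, the test needs 21 successes of 25, and exact power is 68.2%.
- Margin of error: 1.96 × 0.0954 = 0.187. This reproduces the statement that "with a sample size of 25 patients, we will have a margin of error of 0.19".

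The SAP gives no power or precision for any continuous scale, so there is nothing to reproduce there.

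**2. Signed-rank test on QMG change.** Inputs: n = 25 (section 4) and two-sided 5% (taking the 5% level in section 3 to apply to the section 2 test as well). The SD of the Week 0 to Week 12 change is not in the SAP and is assumed to be 2.5 to 4 points. Changes were simulated as normal values rounded to whole points. The share of trials with a non-significant result was about:

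| Assumed SD | True mean worsening 1.0 | True mean worsening 1.5 |
|---|---|---|
| 2.5 | 54% | 20% |
| 3 | 65% | 35% |
| 4 | 78% | 58% |

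Repeat runs differed by up to about three percentage points. For a mean worsening of 3 points, power is about 100% at SD 3, 94% at SD 4 and 81% at SD 5. The test is therefore uninformative about modest worsening, not about large worsening.

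**3. Fewer patients.** By the paired t-test at SD 4, power for a 2-point worsening is 67% with 25 patients, 57% with 20 and 44% with 15.

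**4. What an interval adds.** The t-based half-width, close to that of the Hodges-Lehmann interval for roughly normal changes, is 2.064 × SD / √25. This gives 1.03, 1.24 and 1.65 points for SD 2.5, 3 and 4. Two illustrative results show the gain:
- Observed change 0, SD 2.5: interval −1.03 to 1.03.
- Observed worsening 1.2, SD 4: interval −0.45 to 2.85.

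Both are non-significant. The first excludes a mean worsening above about 1 point; the second excludes only one above about 2.9.

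**5. A 3-point rule for the group, checked and rejected.** Suppose maintenance were concluded whenever the upper 95% limit for the median change lay below 3. At SD 3 and a true mean worsening of 1 point, about 76% of simulated trials would be declared maintained. About 35% of all trials would be declared maintained while having fewer than the 21 successes that the primary test needs.

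**The case against.** The strongest reply is that the SAP says nothing false here. A signed-rank test does assess whether scores changed, and the SAP claims no more for it. Maintenance is tested elsewhere: the primary analysis is one-sided, uses the 3-point threshold and carries an interval, and section 3 compares the percentage stable between phases. The QMG test is labelled exploratory. All of this stands and sets the weight of the point.

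A reader might infer that the trial's claim of stability rests on these tests, or that the SAP intends to read a p-value above 0.05 as stability. The text supports neither reading.

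It is also fair that the percentages depend on an assumed SD, that they cover QMG and none of the secondary scales, and that the test rarely misses a 3-point mean worsening at SD 3 to 4. The logic does not depend on the SD: at any SD, a non-significant test alone puts no bound on the worsening.

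A reader might go further and want maintenance concluded whenever the upper limit falls below 3 points. The document does not support that. Its 3 points is a cut-off for an individual patient, and a group median below it can coexist with many individual failures. Step 5 of the working shows that the rule would add a second and more lenient maintenance claim.

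**Conclusion.** The point holds as a reporting improvement. For continuous QMG and the four secondary scales, the signed-rank test is the only planned inference on the size of the Week 0 to Week 12 change, and no interval goes with it. With 25 patients and an assumed SD of QMG change of 2.5 to 4 points, it would be non-significant in about 54% to 79% of trials when the true mean worsening is 1 point, and in about 19% to 59% when it is 1.5 points. These figures assume roughly normal changes and no dropout; with fewer completers the test is weaker. The primary conclusion is unaffected.

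**What to change.** In SAP sections 2 and 3:
- Make the Hodges-Lehmann median change from Week 0 to Week 12, with its 95% confidence interval, the main result for QMG, MG-ADL, MG QOL-15, the MG composite and TSQM.
- Keep the signed-rank p-value as supporting information.
- Add a sentence that a non-significant test is not evidence of stability.
- Label the secondary-scale intervals as completer estimates, since patients who deteriorate are withdrawn and may not contribute.
- Do not add a rule that declares maintenance when the upper limit is below 3 points. The responder analysis should remain the only formal test of maintenance.

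The cost is a few lines of SAP text and one extra output per scale from data already collected. Sample size, visits and the primary analysis do not change.

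### Secondary score tests give no value to patients who leave because they worsened, but carry forward those who leave while doing well or are lost to follow-up

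*SAP*

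**What the plan says.** Section 3 (Analysis of Secondary Outcomes) tests MG-ADL, MG QOL-15, MG composite and TSQM from Week 0 to Week 12 with two-sided signed-rank tests at 5%. The analysis "will primarily be conducted only for those who complete the study".

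An exception follows: "In case of missing values for the MG-ADL, MG QOL-15, and the MG composite score", LOCF supplies Week 12 for patients who decline to continue "even though they were responding well on the treatment (as evidenced by the intermediate measurements) or are lost to follow-up". TSQM is not in that list and has no missing-value rule.

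The same section expects exits for worsening. For the prednisone Fisher's test it says "Those patients who exit the study prematurely due to deterioration before Week 12 will be excluded" from the calculation. It also plans a descriptive comparison: "We will compare between the two phases the percent of subjects meeting the definition of deterioration, worsening, stability and improvement".

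Section 1 (Analysis of Primary Outcome) handles the worsening patients explicitly, but for QMG only. Those with treatment failure or clinical deterioration "will be withdrawn before Week 12 and we will therefore impute for both non-positive responses at Week 12", as a QMG increase above 3 points. The same imputation applies when Week 12 is missing "due to the subject's perception of a worsened condition". Three sets of sensitivity analyses are attached to that endpoint.

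Section 5 (Study Populations) defines the ITT set as patients with at least one SCIg dose and assigns it to the efficacy results. Its paragraph on unscheduled visits requires withdrawal once worsening qualifies as clinical deterioration.

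**The concern.** Two of the three routes out of the study lead back into the secondary tests on the MG scales: stopping while well, and loss to follow-up. The third, leaving because of worsening, does not. Withdrawal on clinical deterioration is mandatory, so the outcome itself decides who is missing.

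In a single-arm switch study these before–after tests are the inferential evidence on whether disease status, as measured by these scales, held after the move from IVIg to SCIg. If patients withdrawn for worsening also tend to worsen on the scale, removing them raises the chance of a spurious improvement and lowers the chance of detecting a real decline. This is a stated rule that works in one direction, not a detail left to the protocol.

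**Working it through.** **Who receives a Week 12 value**

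| Reason Week 12 is missing | QMG (section 1) | MG-ADL, MG QOL-15, MG composite (section 3) | TSQM (section 3) |
|---|---|---|---|
| Stops while responding well | LOCF | LOCF | none |
| Lost to follow-up | LOCF, if responding well | LOCF; as worded, good response may not be required | none |
| Treatment failure or clinical deterioration | increase of more than 3 points | none | none |
| Feels worse | increase of more than 3 points | none | none |

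**Inputs.** From the SAP: n = 25, two-sided signed-rank test, 5% level, visits at Weeks 4, 8 and 12. The SAP gives no withdrawal rate, correlation or power for these tests, so there is no stated figure to reproduce. Everything else is assumed.

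**Visit-level model** (10,000 trials per setting)
- At each visit a withdrawal criterion z and a scale change y (higher = worse) are standard bivariate normal with correlation r. Correlation between visits is 0.7.
- A patient is withdrawn at Week 4 or 8 if z exceeds c. With c = 1.9, 1.5 and 1.25, the mean number withdrawn is 1.2, 2.6 and 4.0 of 25.
- The exact test is run on Week 12 changes. Each tail is nominally 2.5%.
- Simulation error is √(p(1−p)/10,000): 0.16 percentage points at p = 2.5%, 0.31 at 10.7% and 0.5 at 50%.
- Losses to follow-up and stops while responding well are not modelled.

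**No true change: chance of a significant improvement, completers**

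| r | 1.2 withdrawn | 2.6 withdrawn | 4.0 withdrawn |
|---|---|---|---|
| −0.3 | 2.0% | 1.5% | 1.1% |
| 0 | 2.6% | 2.3% | 2.5% |
| 0.3 | 2.9% | 4.2% | 4.1% |
| 0.5 | 3.5% | 5.2% | 6.3% |
| 0.8 | 4.1% | 7.3% | 10.7% |

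With all 25 patients it is 2.3–2.7%. At r = −0.3 the bias reverses: false worsening is 3.0, 3.7 and 4.6%.

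**True worsening of 0.5 SD: chance of detecting it** (withdrawal rate held fixed)

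| Analysis | 1.2 withdrawn | 2.6 withdrawn | 4.0 withdrawn |
|---|---|---|---|
| Same number removed at random | 61.4–62.1% | 58.6–59.2% | 54.2–56.3% |
| Completers, r = 0.3 | 57.4% | 52.6% | 45.4% |
| Completers, r = 0.5 | 56.7% | 47.8% | 39.5% |
| Completers, r = 0.8 | 54.5% | 43.2% | 32.8% |

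All 25 patients give 63.5–65.0%. The gap from there to random removal is lost sample size: about 9 points with 4.0 withdrawn. The gap from random removal to completers is selection:
- 4.0 withdrawn: from 54.2 − 45.4 ≈ 9 points (r = 0.3) up to 56.3 − 32.8 ≈ 24 points (r = 0.8).
- 1.2 withdrawn: from 61.4 − 57.4 = 4 points up to 62.1 − 54.5 ≈ 8 points.

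**Upper bound** (20,000 trials, exactly the k patients with the largest z dropped, no true change). False improvement for k = 1, 2, 3, 4:
- r = 0.3: 3.3, 3.9, 4.7, 5.3%
- r = 0.5: 4.0, 5.4, 7.1, 8.8%
- r = 0.8: 5.1, 9.1, 13.0, 18.8%

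**The remedies in the visit-level model** (no true change, r = 0.3 to 0.8, over all three withdrawal rates)

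| Handling of the withdrawn | False improvement | False worsening |
|---|---|---|
| Score at withdrawal visit carried forward | 1.3–2.1% | 2.6–4.7% |
| Same, but a random half take worst-change rank | 0.6–2.0% | 3.2–8.0% |
| All take worst-change rank | – | 3.5–16.8% |

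**The case against.** The completer basis is declared openly, the tests are secondary, and the primary endpoint counts worsening patients as failures, with sensitivity analyses. Section 1 adds "Although we do not expect many missing observations at Week 12 of the SCIg phase". With about one withdrawal, the excess false improvement is only 0.4 to 1.6 points (2.9 − 2.5 to 4.1 − 2.5). The larger figures need about four withdrawals and a strong correlation. All of this stands, and it limits the weight of the point.

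The direction is partly assumed. The deterioration definition lies outside this document. Section 3 ties improvement to QMG or MG-ADL, which supports a positive correlation for MG-ADL indirectly; for MG QOL-15 and MG composite it is plausible but undocumented. For TSQM no direction can be claimed.

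A specific rule in section 3 may be read as overriding the general ITT sentence in section 5. That reading is reasonable, but the SAP does not say so. The word *primarily* hints at another analysis, yet none is specified for these scores beyond the selective LOCF.

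The deterioration percentages keep these patients visible, and LOCF for loss to follow-up may catch some who were worsening. Neither brings patients withdrawn for worsening into the signed-rank tests.

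Finally, the remedy has a bias of its own: the worst-rank fallback can raise false worsening to about 8%. That is why it is confined to patients with no recorded score. It is not a reason to keep a rule that departs from section 1's handling of the same patients.

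**Conclusion.** The concern holds. For MG-ADL, MG QOL-15 and MG composite, section 3 restores patients who leave while doing well or are lost to follow-up and leaves out those who leave because they worsened. That the rule is one-sided is certain from the text.

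The size and direction of the bias are conditional. They rest on an assumed normal model, an assumed withdrawal rate, and a positive correlation between withdrawal and scale change. On those terms the effect is small with about one withdrawal and material with about four: false improvement of 4.1–10.7%, and power to detect a 0.5 SD worsening of 33–45% instead of about 64%. It vanishes with no such withdrawals or zero correlation, and reverses if the correlation is negative.

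For TSQM the finding is only that missing values have no rule. The SAP should be changed, but the primary conclusion is not threatened.

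**What to change.** In section 3:
- Run the MG-ADL, MG QOL-15 and MG composite signed-rank tests in the ITT set.
- Where Week 12 is missing because of treatment failure, clinical deterioration or perceived worsening, use the score from the withdrawal or last visit if recorded; otherwise assign the worst-change rank.
- Keep the existing LOCF rule for the other missing values.
- Report completers only, and worst rank for all worsening exits, as sensitivity analyses.
- Label the TSQM test completer-only and report the number missing with reasons. If intermediate TSQM scores exist, the alternative is one symmetric rule: last available score for every early leaver, whatever the reason.
- State how these analysis sets relate to the ITT sentence in section 5.

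The cost is SAP wording and a little programming. Estimates become slightly less favourable to SCIg and the tests somewhat conservative, by the amounts shown for the remedies above. The SAP does not say which scales are scored at withdrawal, so the fallback is needed; the fewer patients who require it, the smaller its bias.
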